## Proliferation Markers

Human endometrial cancer cell lines ECC-1 and Ishikawa, when treated with metformin, showed decreased proliferation and decreased hTERT expression relative to non-treated cells. In women treated with metformin to manage PCOS, sera from PCOS women after 6 months of metformin significantly decreased the invasive properties of ECC-1, in part, by attenuating pro-inflammatory NF- $\kappa$ B expression and activation of Akt and Erk1/2 pathways. Further, the increase in progesterone receptor expression in metformin-treated Ishikawa and HEC-1B cells was associated with pathways targeted by adipokines and insulin.

In this pilot study, we will evaluate the effect of metformin on endometrial tumor-cell proliferation and apoptosis, obesogenic and pro-tumorigenic marker gene expression, and anti-oncogenic micro-RNA (miR) expression. miRs are potentially important regulators of expression of tumor-enhancing and tumor-suppressing pathway components. Endometrial tumors and adjacent non-involved tissues will be obtained at surgery. Tissues will be processed for histopathology and immunohistochemistry, and frozen in liquid nitrogen for RNA and protein analyses. Fasting blood sera will be obtained prior to and after the 14-to-21-day treatment period for measurement of insulin, adiponectin, leptin, and IGF-1 levels. Fixed tumor and 'normal' tissues will be analyzed for markers of proliferation (Ki67; phospho-histone H3) and apoptosis (TUNEL), and for expression of estrogen receptor (ER) $\alpha$ , progesterone receptor (PR), and tumor suppressor PTEN by immunohistochemistry. Isolated tissue RNAs will be assessed for PR, PTEN, ER $\alpha$ , KRAS, and hTERT transcripts by quantitative RT-PCR. Protein extracts will be evaluated by Western immunoblotting for PR, PTEN, total and activated Akt and Erk 1/2, and insulin receptor expression. Sera from both groups at both time points will also be subjected to analysis using miR-profiling arrays. Data obtained from analyses of all biological endpoints will be compared using standard statistical procedures.

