### **Trial Design**

This is a single-center, two-arm, open-label, randomized proof-of-concept pilot study to ascertain the therapeutic potential of metformin in obese women with Type I endometrial cancer. Forty non-diabetic obese subjects with confirmed stage I or II adenocarcinoma of the endometrium will be recruited from the University of Arkansas for Medical Sciences (UAMS).

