#### **A. Method of assigning subjects to treatment groups.**

Subjects will be assigned randomly to one of two groups. Group 1 will receive treatment with metformin, while Group 2 will receive no treatment. Subjects assigned to Group 1 will be administered oral metformin at 500 mg twice a day for 14-21 days followed by surgery. These doses are therapeutic, and will permit patients to undergo their surgical therapy within an appropriate time frame.

Subject eligibility will be established before treatment randomization. Once a subject's eligibility is determined, the Research Staff will be notified to implement the randomization process. Randomization will be completed when the Research Staff receives a copy of the signed consent and the physician's orders for study agent to be dispensed.

To minimize imbalance between treatment arms, the randomization procedure will employ a stratified block randomization with randomly chosen blocks of size 2, 4, and 6, and with BMI as the stratification factor. Randomization will be conducted using sealed envelopes located at the Cancer Clinical Trials Office (CCTO). There will be two sets of consecutively numbered envelopes, one set for subjects with BMI from 30 to 39.9 and one set for subject with BMI of 40 or higher. At each randomization, the lowest numbered envelope will be chosen. The Research Staff will open the envelope and assign the subject to the treatment arm based on the contents of the envelope. The appropriate treatment will then be dispensed to the subject.

Methods for ensuring blinding.

Not applicable: this is an open-label study.

Methods for unblinding the study.

Not applicable: this is an open-label study.

Procedure for unblinding in case of medical emergency.

Not applicable: this is an open-label study.

Metformin will be administered to patients (randomized to receive metformin) for a minimum of 14 days and a maximum of 21 days, representing the typical time interval between confirmation of tumor diagnosis and surgical resection. Following surgical resection, any unused study drug will be returned to the physician at the time of the subject's first post-operative visit.

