**B. Blood Draws and Laboratory Tests**

Blood will be drawn from each subject, approximately 18 mL in purple top vacutainers, prior to treatment assignment (if not preformed previously as conventional care) and after completion of the therapy at the time of surgery. The blood sample below will be subjected to the following tests at the UAMS Clinical Laboratory:

- a) A comprehensive metabolic panel (glucose, calcium, albumin, total protein, sodium, potassium, CO2, chloride, BUN, creatinine, ALP, ALT, AST and total bilirubin), to be performed prior to starting treatment only.
- b) A lipid panel (cholesterol, HDL-C, LDL-C, triglycerides), to be performed both prior to treatment assignment and at the time of surgery.
- c) Determination of HbA1c, to be performed both prior to treatment assignment and at the time of surgery.

The blood samples listed below will be utilized for correlative laboratory studies in the research laboratory of [name] at the UAMS Biomed Bldg. Aliquots of each blood sample will be centrifuged to separate out the plasma portion. Plasma will be stored at -80°C in the Co-Investigator's lab until analysis is performed.

The following biomarkers will be assayed in the plasma samples collected at baseline and at the time of surgery through enzyme-linked immunosorbent assays (ELISA) or multiplex assays. All of these tests will be performed by laboratory personnel in [name] lab:

- a) Insulin
- b) Leptin
- c) Adiponectin
- d) IGF-I and IGF-II

Remaining plasma samples will be subjected to global profiling of miRs and mRNAs to evaluate/validate the relative expression of specific candidate metformin-regulated miRs and mRNAs ([name] lab). miR and mRNA levels will be determined using quantitative SYBR green-based real time reverse transcriptase polymerase chain reaction (RT-PCR) assays and a microarray platform. These tests will be performed in [name] laboratory by his personnel and/or by commercial providers of microarray profiling services.

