### **C. Tissue Specimens and Laboratory Tests**

A sample of tumor with adjacent normal mucosa will be obtained after surgery from the Pathology department from the tissue remaining after normal gross and histological assessments.

Fresh tissue samples will be transported by designated research personnel to [name] laboratory at the UAMS Biomed Bldg. Fixed tumor and 'normal' tissues will be subjected to IHC for markers of proliferation (*Ki-67*, phospho-histone H3), and apoptosis (TUNEL, cleaved caspase-3). Tumor (and 'normal') tissues will also be examined by Western blot and/or ELISA for expression levels of FASN, total and phosphorylated insulin receptors, and total and phosphorylated IGF-I receptors. Total and phosphorylated AMPK levels will be assessed by IHC or Western blot. Lastly, tissues will be used for miR and mRNA profiling.

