## **Outcome Measures**

### **A. The primary endpoints** of this study consist of the following:

- a. IHC-based tissue markers of proliferation: Ki67, phosphorylated histone H3, estrogen receptor (ER), progesterone receptor (PR), and telomerase (hTERT).
- b. IHC-based tissue markers of anti-proliferation and apoptosis: PTEN, KLF9, cleaved caspase-3, and TUNEL staining.
- c. IHC-based tissue markers of insulin-mediated signalling: total and phosphorylated versions of Akt, Erk1/2, AMPK, and receptors for Insulin, IGF-I, and IGF-II.
- d. Meformin-related adverse events.

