## Data Handling and Recordkeeping

The PI will carefully monitor study procedures to protect the safety of research subjects, the quality of the data and the integrity of the study. The data will be kept in an electronic database in the office of clinical trials at the Winthrop P. Rockefeller Cancer Institute. Only the PI and Co-I, CRAs, regulatory personnel, biostatistician and lab personnel performing the analyses will have access to the data. In the event that a subject fails screening, only the eligibility criteria case report form will be completed.

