Official Title: A Randomized Pilot Study to Evaluate the Effects of a Short Course of Metformin versus No Therapy in the Period Prior to Hysterectomy for Grade 1-2 Adenocarcinoma of the Endometrium in Obese Non-Diabetic Women

Protocol - Statistical Analysis Plan, v10 dated 5/24/2016

Data Handling and Recordkeeping

The PI will carefully monitor study procedures to protect the safety of research subjects, the quality of the data and the integrity of the study. The data will be kept in an electronic database in the office of clinical trials at the Winthrop P. Rockefeller Cancer Institute. Only the PI and Co-I, CRAs, regulatory personnel, biostatistician and lab personnel performing the analyses will have access to the data. In the event that a subject fails screening, only the eligibility criteria case report form will be completed.

Monitoring

Medical Monitor: The Medical Monitor, Principal Investigator and study staff will meet quarterly, once the PI has monitored the data, to review safety data (adverse events, serious adverse events and other scientific observations).

Study Monitor: The study will be monitored to ensure that the rights and well-being of human subjects are protected, that the data are accurate, complete and verifiable from source documents and that the trial is conducted in compliance with currently approved protocol/amendments on a quarterly basis.

Statistical Considerations

General approach: For each tissue endpoint, the tumor-NTU difference will be calculated in each patient as the paired difference in values between tumor and adjacent NTU tissue. For each blood endpoint, the endpoint response to treatment will be calculated in each patient as the paired difference between post-study and pre-study values. All data will be summarized by treatment arm as the mean, standard deviation (SD), median, and range, and will be graphed as box plots. Tumor-NTU differences and endpoint responses will be compared against zero via signed-rank test within each treatment arm. Treatment arms will be compared to each other for differences via Wilcoxon rank-sum tests, with additional details provided below. All statistical comparisons will be two-sided, and will employ a 10% alpha to reduce Type II error in this pilot proof-of-concept study.

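### Blinding is set aside as not applicable, so nothing in the plan keeps treatment arm from the laboratory staff who measure and score the tissue primary endpoints

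*Protocol*

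**What the plan says.** The Protocol describes the trial in these words: "This is a single-center, two-arm, open-label, randomized proof-of-concept pilot study". In Trial Design, section A, the entry under Methods for ensuring blinding reads in full "Not applicable: this is an open-label study". The same answer stands under the two headings on unblinding that follow.

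On access, Protocol, Data Handling and Recordkeeping, states: "Only the PI and Co-I, CRAs, regulatory personnel, biostatistician and lab personnel performing the analyses will have access to the data". The SAP repeats the rule, including the clause "lab personnel performing the analyses will have access to the data". Neither document excludes treatment assignment from that access.

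On samples, Trial Design, section B, says "Plasma will be stored at -80°C in the Co-Investigator's lab until analysis is performed". Section C says "Fresh tissue samples will be transported by designated research personnel to" a research laboratory, whose name is removed from the public text. Both sections list assays. Neither mentions a sample code, a masked reader or a scoring rule.

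On endpoints, Outcome Measures, section A, labels all three tissue groups of primary endpoints as IHC-based. The first is "IHC-based tissue markers of proliferation: Ki67, phosphorylated histone H3, estrogen receptor (ER), progesterone receptor (PR), and telomerase (hTERT". The fourth primary group is adverse events.

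**The concern.** A trial against no treatment cannot blind its patients, but it can still blind its laboratory. The plan treats the two as one question and answers both with the open-label label.

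The tissue primary endpoints are laboratory measurements, and several are read from slides. If the person who stains, selects fields, scores or quantifies knows which patients took metformin, the readings may drift with that knowledge. The rank-sum test cannot tell such a drift from a drug effect.

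Nothing elsewhere in the plan would expose it. The between-arm tissue comparison uses values at surgery with no baseline, and pre-study tissue is collected only if available (Study Calendar, note i). A masked re-read afterwards would need retained slides or blocks, and the plan makes no provision for keeping them. The results are meant for publication and for federal funding applications (Dissemination of Data), so a spurious signal would have consequences.

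**Working it through.** **1. Is masked assessment provided anywhere?**

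| Place | What it provides |
|---|---|
| Protocol, Trial Design A, Methods for ensuring blinding | Declared not applicable |
| Protocol, Trial Design B (plasma) | Storage and assays; no code, no masking |
| Protocol, Trial Design C (tissue) | Transport and assays; no code, reader or scoring rule |
| Protocol and SAP, Data Handling and Recordkeeping | Access for the Co-Investigator and assay staff; no exclusion for arm |
| Protocol and SAP, Statistical Considerations | Direct between-arm tests of tumor values and of NTU values |

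The answer is no. The text does not say that assessors are told the arm. It only fails to prevent it.

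**2. Which primary markers are most exposed?** Proliferation Markers and Trial Design C together name a slide-based method for seven: Ki67, phospho-histone H3, TUNEL, cleaved caspase-3, ER-alpha, PR and PTEN (the last by "tumor suppressor PTEN by immunohistochemistry"). Several others go to Western blot or ELISA, and AMPK to IHC or Western blot. No scoring method is stated for any marker.

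**3. The plan's own power figure.** Inputs from Sample Size and Power: 20 per arm, difference 1.0 SD, two-sided alpha 0.10, stated power 91.6%. Scaling n by the rank-sum test's efficiency under normality gives 20 × 3/π = 19.1 per arm. Noncentral-t power is then 91.7%, or 91.6% with n truncated to 19. The figure reproduces, and masking would not alter it.

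**4. What an arm-linked shift would do (illustration).** The documents give no size for reader bias, so the shift b is an assumption and is shown over a range. Model: normal data, unit SD, true effect zero, b added to every reading in one arm, 20 per arm.

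The exact two-sided 10% rank-sum test has 20 × 20 = 400 pairs. It rejects if U ≤ 138 or U ≥ 400 − 138 = 262, and its exact size is 0.0965.

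The rejection rate was simulated with 200,000 trials per row; the Monte Carlo standard error is at most √(0.25/200,000) = 0.0011. A hand check uses

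rate ≈ Φ(−z + δ) + Φ(−z − δ), with δ = b × √((20/2) × 3/π) = 3.090b and z = 1.662 (two-sided 0.0965).

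For b = 0.2, δ = 0.618 and the rate is Φ(−1.044) + Φ(−2.280) = 0.148 + 0.011 = 0.160 from unrounded terms.

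| Assumed shift b (SD) | Simulated false-positive rate | Hand approximation |
|---|---|---|
| 0 | 9.7% | 9.6% |
| 0.1 | 11.2% | 11.2% |
| 0.2 | 15.7% | 16.0% |
| 0.25 | 19.0% | 19.4% |
| 0.3 | 23.0% | 23.6% |
| 0.5 | 44.1% | 45.4% |

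The large-sample version of the test, simulated separately with 40,000 trials per row, gives 9.8%, 11.1%, 15.6%, 22.8% and 44.2% at shifts of 0, 0.1, 0.2, 0.3 and 0.5 SD.

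**The case against.** The best reply is that this is silence, not error. The blinding entry sits in the section on treatment assignment, where it is a correct statement about treatment. The access rule is a confidentiality limit and does not say which fields each role sees. The randomization envelopes are at the CCTO, while the assays are done in another building. The tissue laboratory's name is removed, so the text does not show that the Co-Investigator's laboratory scores the tissue. Coding might be described in consent pages that are not public. Some assays leave less room for judgement than slide reading, and the assumed shifts have no source in the documents. Mixed batches also mean holding samples until enough have accrued.

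Much of this is fair as a limit on the claim. It is not shown that any assessor will know the arm, that the Co-Investigator scores tissue, or that bias of any given size will occur. The concern weighs most on slide reading. At a shift of 0.1 SD the harm is small.

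The core is untouched. An explicit heading on blinding was answered without separating treatment from assessment. Separate buildings are not masking, and confidentiality coding alone would not override an access rule with no exclusion for arm. Pilot status and a 10% alpha accept more chance findings; they are no reason to accept avoidable bias. Mixed batches suit a plan that already freezes plasma and tissue and compares arms only after all samples are analysed.

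**Conclusion.** The concern holds. The available text has no masked laboratory assessment for the tissue primary endpoints, and open-label treatment does not require that gap.

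The actual size of any bias cannot be derived from the documents. If a systematic shift of 0.2 to 0.5 SD arose, the false-positive rate per marker would be about 16% to 44%, against 9.7% for the exact test with no shift. Those rates assume normal data, no true effect, the same shift in every reading of one arm, and 20 evaluable patients per arm.

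This should be corrected before any scoring begins. It does not invalidate the design, and it does not touch the sample size calculation.

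**What to change.** 1. **Protocol, Trial Design A.** Under Methods for ensuring blinding only, replace the present entry with: *Treatment is open-label; laboratory assessments of tissue and plasma endpoints are masked to treatment arm.* The two entries on unblinding treatment can stay.
2. **Protocol, Trial Design B and C.** Label each sample with a study code that carries no arm information before it reaches the research laboratory; for tissue, do this at the handover from Pathology. Hold the code list at the CCTO, which already keeps the randomization envelopes.
3. **Assay runs.** Run and read samples from both arms in mixed batches. Mix time points too where both exist: plasma, and tissue only where a pre-study sample is available.
4. **Data Handling and Recordkeeping, Protocol and SAP.** Add: *Laboratory personnel, and the Co-Investigator where that laboratory performs or scores the assays, have no access to treatment assignment until scores are locked and sent to the biostatistician.*

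The cost is low: wording in both documents, one coding step at handover, and some scheduling of batches. Staff, assays, sample size, alpha and power are unchanged. If the laboratory already works masked, the change only records it.

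This would largely remove reader bias from the laboratory endpoints. It does nothing for open-label bias in the adverse-event primary endpoint, which remains a limitation to state.

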**B. Blood Draws and Laboratory Tests**

Blood will be drawn from each subject, approximately 18 mL in purple top vacutainers, prior to treatment assignment (if not preformed previously as conventional care) and after completion of the therapy at the time of surgery. The blood sample below will be subjected to the following tests at the UAMS Clinical Laboratory:

- a) A comprehensive metabolic panel (glucose, calcium, albumin, total protein, sodium, potassium, CO2, chloride, BUN, creatinine, ALP, ALT, AST and total bilirubin), to be performed prior to starting treatment only.
- b) A lipid panel (cholesterol, HDL-C, LDL-C, triglycerides), to be performed both prior to treatment assignment and at the time of surgery.
- c) Determination of HbA1c, to be performed both prior to treatment assignment and at the time of surgery.

The blood samples listed below will be utilized for correlative laboratory studies in the research laboratory of [name] at the UAMS Biomed Bldg. Aliquots of each blood sample will be centrifuged to separate out the plasma portion. Plasma will be stored at -80°C in the Co-Investigator's lab until analysis is performed.

The following biomarkers will be assayed in the plasma samples collected at baseline and at the time of surgery through enzyme-linked immunosorbent assays (ELISA) or multiplex assays. All of these tests will be performed by laboratory personnel in [name] lab:

- a) Insulin
- b) Leptin
- c) Adiponectin
- d) IGF-I and IGF-II

Remaining plasma samples will be subjected to global profiling of miRs and mRNAs to evaluate/validate the relative expression of specific candidate metformin-regulated miRs and mRNAs ([name] lab). miR and mRNA levels will be determined using quantitative SYBR green-based real time reverse transcriptase polymerase chain reaction (RT-PCR) assays and a microarray platform. These tests will be performed in [name] laboratory by his personnel and/or by commercial providers of microarray profiling services.

### **C. Tissue Specimens and Laboratory Tests**

A sample of tumor with adjacent normal mucosa will be obtained after surgery from the Pathology department from the tissue remaining after normal gross and histological assessments.

Fresh tissue samples will be transported by designated research personnel to [name] laboratory at the UAMS Biomed Bldg. Fixed tumor and 'normal' tissues will be subjected to IHC for markers of proliferation (*Ki-67*, phospho-histone H3), and apoptosis (TUNEL, cleaved caspase-3). Tumor (and 'normal') tissues will also be examined by Western blot and/or ELISA for expression levels of FASN, total and phosphorylated insulin receptors, and total and phosphorylated IGF-I receptors. Total and phosphorylated AMPK levels will be assessed by IHC or Western blot. Lastly, tissues will be used for miR and mRNA profiling.

### **D. Subject Data**

Subject data to be obtained and recorded will consist of the following:

- a) Patient characteristics: gender; age; BMI; race and ethnicity; smoking status (including approximate packs per day for current and former smokers); alcohol intake.
- b) Tumor characteristics: tumor stage; tumor differentiation status (well, moderate, poor); lymph node involvement; depth of invasion; tumor margins.
- c) Comprehensive metabolic panel: glucose, calcium, albumin, total protein, sodium, potassium, CO2, chloride, BUN, creatinine, ALP, ALT, AST and bilirubin.
- d) Lipid panel: cholesterol, HDL-C, LDL-C, triglycerides.
- e) Plasma markers: plasma HbA1c; plasma insulin; plasma leptin; plasma adiponectin; plasma IGF-I; plasma IGF-II; plasma profiles of miR and mRNA.

- f) Tissue markers: endometrial cancer and uterine apoptotic indices; endometrial cancer and uterine proliferative indices; endometrial tumor miR and mRNA profiles; endometrial (adjacent NTU) miR and mRNA profiles.

#### **E. Subject Diary**

A subject who is randomized to metformin will receive a diary on Day 1. The subject is to record the date and time of self-administration of the study drug. The diary will be reviewed weekly by members of the study team via telephone for compliance. The diary will be collected at the subject's post-operative visit.

